4.3 B - Screen failures

Subjects are pre-screened based on the information available from the institutional standard of care. For subjects who appear to be candidates for the study based on this available information, IC signature and other study-specific screening procedures take place prior to enrollment. A subject who withdraws IC before enrollment or who fails to meet

INSTANT Study Clinical Study Protocol

Study no. FLE-002

Version 8.0 EU-1 Page: 47 of 117

inclusion/exclusion criteria before enrollment is defined as a screen failure. No further clinical follow-up is performed for screen failed subjects unless they are re-screened and enrolled.

Subjects who are enrolled but who do not receive study drug (e.g., due to spontaneous conversion of their AF to SR prior to dosing) are considered early terminations; refer to Section 5.5 B.

5 B – Treatment

5.1 B - Study treatments

Study treatment in Part B consists of a 120 mg eTLD ($2 \times 60 \text{ mg}$) FlecIH-103 inhalation solution repeat dose regimen. Specific instructions for the administration of study treatments are provided to the sites in the Instructions for Use (IFU). Also refer to Section 5.3.4 B for more treatment guidelines.

5.1.1 B - Repeat dose regimen

'Dose/inhale to conversion':

2 x 60 mg eTLD (FlecIH-103) for 120 mg eTLD (75 mg/mL concentration)

Dosing in a 'dose/inhale to conversion' regimen continues until the conversion of AF to SR is observed for ≥ 1 minute, or until the assigned dose is completed, whichever comes first.

5.2 B - Treatment assignment

After the IC has been signed, the investigational site enters the subject in the eCRF to obtain a unique subject identification number (SID) (if not already obtained during pre-study screening). Subjects may be enrolled at the end of the AF monitoring period provided they meet all the inclusion criteria and none of the exclusion criteria (note, AF monitoring must continue for at least 45 minutes prior to dosing, regardless of enrollment time).

Subjects are assigned to a 120 mg eTLD (2 x 60 mg) FlecIH-103 repeat dose regimen (N = approximately 25 subjects).

5.3 B - Identity of study drug(s)

5.3.1 B – Description

Study drug is supplied as a 4.7 mL of sterile FlecIH-103 (75 mg/mL flecainide acetate) in a 6-mL clear glass vial, with a grey rubber stopper, and sealed with an aluminum crimp.

INSTANT Study

Clinical Study Protocol

Study no. FLE-002

Version 8.0 EU-1 Page: 48 of 117

5.3.2 B - Labeling and packaging

FlecIH-103 is labeled according to the requirements of local regulatory guidelines. Label text is approved according to the Sponsor's procedures. A description of FlecIH-103 is given in Table 1 below.

A system of numbering in accordance with all requirements of Good Manufacturing Practice (GMP) is used, ensuring that each dose of FlecIH-103 can be traced back to the respective bulk batch of the ingredients. Lists linking all numbering levels are maintained by the Sponsor. A complete record of batch numbers and expiry dates of FlecIH-103 as well as the labels is maintained in the Sponsor's study file.

Table 1 - Identity of investigational drug: FlecIH-103

	75 mg/mL concentration
Active ingredient or INN	Flecainide acetate
CAS No.	54143-56-5
Material name	FlecIH-103 (flecainide acetate inhalation solution)
Dosage(s)	120 mg: 2 x 60 mg eTLD
Color of the vial	Clear
Composition	Active ingredient: Flecainide acetate
	Excipients: water for injection, Glacial Acetic Acid, hydroxypropyl
	β-cyclodextrin, Sodium Saccharin, and Sodium Hydroxide
Concentration	75 mg/mL
Type of packaging	Glass vial
Content	1 sealed vial of 4.7 mL

5.3.3 B - Preparation

The FlecIH-103 is supplied in glass vials. The clinical site will prepare the dose to be administered by withdrawing the required volume of the study drug from the vial(s) using a syringe with needle and then dispensing the study drug into the nebulizer cup(s). In order to maintain sterility, the study drug must be administered within 4 hours of dispensation into the nebulizer cup. Detailed instructions for dose preparation are outlined in the Pharmacy Manual.

5.3.4 B – Administration

Subjects will be dosed with 120 mg eTLD (2 x 60 mg) FlecIH-103 (75 mg/mL) inhalation solution: 2 inhalations of 3.5 minutes each, separated by a 1-minute break ('dose/inhale to conversion'). Dosing in a 'dose/inhale to conversion' regimen continues until the conversion of AF to SR is observed for \geq 1 minute, or until the full dose is completed, whichever comes first.

For the administration of study drug, the following procedures are to be performed:

Study no. FLE-002

Version 8.0 EU-1 Page: 49 of 117

1. The subject must be seated in an upright position in a chair or adjustable bed from approximately 30 minutes prior to the start of inhalation up to completion of dosing, at which point subjects may return to a semi-recumbent position. A height-adjustable table must be placed in front of the subject (e.g., overbed table on casters), whereby the subject can rest his/her arms during the inhalation regimen. The set up at the site will allow for subject to remain in this upright sitting position while connected to the cardiac monitoring system and while blood samples are collected during the self-administration of the inhalation solution.

NOTE: Subjects may be placed in a semi-recumbent, supine, or other position as needed for an adverse event, at the discretion of the investigator. These occurrences will not constitute a protocol deviation.

- 2. The subject is given instructions from study personnel on how to inhale the study drug according to the IFU.
- 3. The subject is required to use a nose clip to seal off their nostrils during inhalation, unless the subject refuses.
- 4. The subject may practice the inhalation procedure (without flecainide) prior to starting the inhalation of study drug.
- 5. The inhaler must be connected to medical compressed air that is set at a steady flow rate of 5 L/min.
- 6. The subject shall be informed prior to the start of the inhalation about the potential to experience throat discomfort, bad taste, and the impact of the sensation caused by the vapors being inhaled.
- 7. If not contraindicated, a topical oral anesthetic (e.g., containing lidocaine or phenol) spray (e.g., Medica, Chloraseptic) or lozenge (e.g., Trachitol, Cepacol) may be used by the subject to prophylactically mitigate the discomfort or pain associated with the inhalation and thereby improve the tolerability.
- 8. The subject inhales the study drug using a fully assembled AeroEclipse® II BAN provided by the study nurse.
- 9. Site staff shall closely observe the subject during inhalation to ensure that the subject only inhales and exhales through the mouth.
- 10. Once the inhalation rhythm is established, the subject should not remove the mouthpiece of the inhaler from the mouth during the entire inhalation time. If the subject removes the mouthpiece of the inhaler from their mouth for any reason/cause (e.g., cough, excessive saliva, etc.) and the inhalation is interrupted for > 30 seconds, then the inhalation time may be extended by the duration of the interruption if conversion of AF to SR is not achieved during inhalation. During the entire inhalation procedure, the nurses shall remain vigilant and ready to assist the subjects to successfully complete each inhalation period.
- 11. Once conversion of AF to SR is observed on telemetry, the time of the observation should be recorded as the time of conversion; however, the subject must continue dosing for at least 1 minute to confirm that SR is stable. If SR does not remain stable

INSTANT Study Clinical Study Protocol

Study no. FLE-002

8.0 EU-1 Page: 50 of 117 Version

for ≥ 1 minute, the subject should continue dosing according to the assigned regimen and conversion to SR will not be reported.

- 12. The subject's right to early terminate inhalation of study drug, for whatever reason/cause, shall not be infringed upon.
- 13. If a subject experiences difficulty in following the instructions for the inhalation procedure, this must be recorded in the eCRF along with the reason.
- 14. If an unexpected event is observed during the inhalation procedure, this event/observation must be recorded in the eCRF (e.g., liquid dripping from the inhaler, fugitive aerosol, etc.).

Additional instructions for the inhalation of the study drug are provided to the sites in the IFU.

5.3.5 B – Shipment, receipt and storage

When a drug shipment is received, the Investigator or designee must check the amount and condition of the drug, check for appropriate local language on the label, check the drug expiration date, and provide confirmation of receipt of the study drug. Problems with drug shipments must be reported to the site Monitor as soon as possible.

Drug supplies are stored at the investigational site in accordance with GCP and GMP and must be stored in a secure, limited-access storage area protected from light and under the recommended storage conditions. All drug supplies shall be stored at 15°C to 25°C (59°F to 77°F) as measured by a min/max thermometer. Excursions to 2°C to 40°C (36°F to 104°F) shorter than a week in duration are permitted. Excursions to 30°C at the site are allowed in accordance with USP <659> guidance. Temperature measurement shall be recorded daily on a temperature log, excluding weekends and holidays. The Sponsor must be notified as soon as possible in the event of any temperature excursion, with the exception of those permitted as described above. The site-relevant elements of special storage conditions, complete batch numbers, and expiry dates are available in the Investigator site file.

5.3.6 B - Drug accountability

Inhalation of study drug is performed under Principal Investigator (PI) or designee supervision. Pertinent information and data on the administration of study drug shall be captured by the site staff in the eCRF. All materials supplied, namely study drug and hand-held inhaler device (AeroEclipse® II BAN), are intended for use in this study only and shall not be used for any other purpose.

The PI or designated trained site staff are responsible for assuring the retrieval of all study supplies needed for the subjects. The pharmacy dispenses the study drug and the Investigator oversees the subject's inhalation and ensures the study drug is only administered according to the procedures described in this study protocol.

INSTANT Study Clinical Study Protocol

Study no. FLE-002

Version 8.0 EU-1 Page: 51 of 117

Study drug administration is documented in the relevant module of the eCRF and other study drug records. The PI at the site is responsible for oversight of the investigational product accountability, reconciliation and record maintenance at the investigational site. In accordance with all applicable regulatory requirements, the PI and/or designated trained staff at each site must maintain investigational product accountability records throughout the course of the study. The amount of investigational product received, administered to study subjects and unused must be documented in study records. Following drug accountability and reconciliation by the Monitor, destruction (if any) of study drugs must be properly documented according to the Sponsor's specified procedures. Re-supply of study drug is made upon request to the investigational product supply vendor. The drug accountability process is described in further detail separately in the Pharmacy Manual. Written instructions on medication destruction are made available to the clinical sites as applicable.

5.4 B – Non-study therapy

5.4.1 B - Prior and concomitant medication

Prior medications that the subject has taken within 30 days of enrollment and the subject's alcohol use are recorded in the eCRF. Medications taken by the subject prior to enrollment or at any time during the study, including adjunct therapy or medical devices, are regarded as prior and/or concomitant medications/treatments and must be documented on the appropriate pages of the eCRF throughout the study and until the final contact with the subject, i.e., EOS.

If the subject experiences an AE, information on concomitant medications taken within the past 30 days needs to be evaluated when considering causal relationship (Section 17.2.2.3).

The concomitant use of Class II and Class IV AADs, i.e. beta-blockers and calcium channel blockers *is allowed* throughout the study.

Concomitant use of the following therapies is *not allowed*:

- Treatment with Class I and any Class III AADs within 1 week before enrollment (except Amiodarone, which is not allowed within 12 weeks before enrollment);
- Concomitant pharmacological or electrical cardioversion up to 90 minutes post completion of dosing; refer to Section 5.4.2 B;
- Concomitant treatment with sotalol, procainamide or ibutilide is not allowed throughout the study;
- Concomitant systemic treatment with drugs that are strong inhibitors of CYP2D6 (e.g., antidepressants, neuroleptics, propranolol, ritonavir, some antihistamines) or CYP 2D6 inducers (e.g., phenytoin, phenobarbital, carbamazepine);
- Investigational drugs (other than the study treatment regimen)
- Bronchodilators from time of consent to start of inhalation of the study drug

INSTANT Study Clinical Study Protocol

Study no. FLE-002

Version 8.0 EU-1 Page: 52 of 117

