 - b) QRS duration ≥ 120 ms or history of previous documented wide QRS tachycardia
 - c) Predominantly (i.e., > 30%) paced heart rhythm
 - d) Ventricular tachycardia (VT, sustained or non-sustained), or excessive premature ventricular complexes (PVCs, > 20 multifocal PVCs per hour), prior to dosing as per site telemetry. Site telemetry should be equipped with an alarm system for VT and PVCs or be continuously visually observed prior to dosing

Concomitant conditions

- 14) Severe renal impairment (eGFR < 30 mL/min/1.73 m²) or on dialysis
- 15) Known medical history of abnormal liver function prior to enrollment
- 16) Uncorrected hypokalemia (defined as serum potassium < 3.6 mEq/L) at screening. If serum potassium result is < 3.8 mEq/L at screening, therapeutic correction (e.g., potassium supplementation) is strongly encouraged, although reassessing the serum potassium level is not required as long as a value of ≥ 3.6 mEq/L is documented at screening.
- 17) Subjects with established pulmonary disease in need of inhalation medication. Subjects with COPD are excluded. Subjects with mild to moderate asthma that are not experiencing active symptoms at screening and whose asthma is well controlled with steroids and/or as-needed administration of a bronchodilator are eligible for the study.

Concomitant and study medication

- 18) Known hypersensitivity to flecainide acetate or any of its active metabolites
- 19) Concomitant therapy with systemic drugs that are strong inhibitors of CYP 2D6 (e.g. antidepressants, neuroleptics, ritonavir, some antihistamines) or CYP 2D6 inducers (e.g. phenytoin, phenobarbital, carbamazepine)

Study no. FLE-002

Version 8.0 EU-1 Page: 46 of 117

20) Treatment with Class I or Class III antiarrhythmic drugs within the last week. Subjects whose current AF episode has been treated with flecainide are eligible if their total cumulative exposure to flecainide (including the study drug to be administered in this study) does not exceed 320 mg within a 24-hour period, per site standard of care.

21) Treatment with amiodarone within the last 12 weeks

Other

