4.2 C - Exclusion criteria

Subjects are NOT eligible to participate in Part C if they meet ANY of the exclusion criteria described in Section 4.2 B.

INSTANT Study Clinical Study Protocol

Study no. FLE-002

Version 8.0 EU-1 Page: 81 of 117

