5.4 C - Non-study therapy

Refer to Section 5.4 B.

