6.1 C - Patient-Led Under Medical Supervision Cardioversion Study: consenting

Consent for the Part C Patient-Led Under Medical Supervision Cardioversion Study may occur in the following ways:

- Potentially eligible subjects from Part A will need to return to the clinic to provide consent and train on the assembly of the device and self-administration of study drug as soon as possible.
- Potentially eligible subjects from Part B may consent to the Part C Patient-Led Under Medical Supervision Cardioversion Study prior to or after discharge and complete the training on the assembly of the device and self-administration of study drug as soon as possible.
- Potentially eligible subjects from the Part C Medically-Led Cardioversion Study may consent to the Patient-Led Under Medical Supervision Cardioversion Study prior to discharge (or return to the clinic within approximately two weeks) and complete the training on the assembly of the device and on self-administration of study drug.

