- Study personnel informs the subject that they must return to the clinic for refresher training at least every 3 months, to avoid early termination from the study. The refresher training may also be completed by telemedicine visit or video conference (e.g., Facetime, Skype), if the site and subject have the capability. Study personnel should schedule a return training visit prior to the subject leaving the clinic.
- Study personnel provides the subject with a training video and instructs the subject
 to watch the video approximately monthly as a refresher. Subjects without access
 to a computer may return to the site monthly to view the training video if
 necessary, or do so via a telemedicine visit or video conference, if the site and
 subject have the capability.
- The study personnel instruct the subject to contact the clinic for return instructions as soon as they feel symptoms of a recurrence of paroxysmal AF. Subjects must return to the clinic and self-administer study drug within 48 hours of the onset of symptoms. If the subject cannot reach the study personnel, they should take the steps to care for themselves as they would normally if they were not participating in this study (e.g., proceed to emergency care or their regular doctor).

Study personnel will contact the subject approximately monthly to check for adverse events and concomitant medications and confirm if subject has viewed the training video.

INSTANT Study Clinical Study Protocol

Study no. FLE-002

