8.0 EU-1 Page: 84 of 117 Version

6.3 C - Patient-Led Under Medical Supervision Cardioversion Study: treatment

After completion of training and becoming certified for patient-led self-administration of study drug, all eligible subjects may return to the clinic for a recurrence of symptomatic paroxysmal AF within 48 hours of the onset of symptoms. Subjects will independently dispense the dose into the nebulizer, reassemble the nebulizer, and self-administer the study drug in the clinic under observation of study personnel. For additional details refer to the IFU. Subjects will selfadminister 120 mg eTLD (2 x 60 mg) FlecIH-103 according to the same dosing regimen in Part B (Section 5.1 B).

Subjects return for patient-led self-administration of study drug for a single recurrent episode(s) of paroxysmal AF within 8 months of signing consent. End of study coincides with Day 5 after the subject's treatment visit, or 8 months after signing consent, whichever comes first.

Before dosing

The following procedures will be performed prior to dosing:

- o The eligibility criteria for Part C are identical to Part B and must be checked and confirmed prior to dosing.
- Blood samples are to be drawn per Investigator discretion to confirm the subject's eligibility at approximately 30 minutes prior dosing, in accordance with the requirements in Section 9.2 C.
- A standard 12-lead ECG (using site's own equipment) is recorded to confirm that the subject's heart rhythm is AF and remains in AF for at least 30 minutes prior to dosing. Once the recording of the ECG is completed and the presence of AF is confirmed, this 12-lead ECG may be disconnected.
- o A baseline PK blood sample is drawn prior to dosing.
- o A symptom-driven physical exam is performed prior to dosing, if deemed necessary by the Investigator.
- o The subject is connected to the telemetry system and to the AECG (Holter) approximately 30 minutes prior to dosing (after being disconnected from the standard 12-lead ECG).
- A single source for the time of all assessments shall be utilized for each patient. For example, if telemetry is used, all assessments for that patient must be recorded from the same telemetry unit. All times shall be reported in a 24-hour format. **NOTE:** The date and time displayed on study Holter monitor AECG must be set to match the date and time of the device used for capturing the time of all assessments, for each subject.
- An IV catheter/cannula is placed for blood sample draws.

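### Section 5.4 C carries Part B's consent-to-inhalation bronchodilator ban unchanged into the patient-led study, where read literally it can last up to 8 months and bars as-needed asthma medication that exclusion criterion 17 allows

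*Protocol*

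**What the plan says.** Protocol Section 5.4.1 B lists therapies whose concomitant use is not allowed. One item is "Bronchodilators from time of consent to start of inhalation of the study drug". The whole of Section 5.4 C, on non-study therapy in Part C, is "Refer to Section 5.4 B".

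On eligibility, exclusion criterion 17 in Section 4.2 B accepts subjects with mild to moderate asthma who have no active symptoms at screening and whose "asthma is well controlled with steroids and/or as-needed administration of a bronchodilator are eligible for the study". Section 4.2 C carries the criteria over: "Subjects are NOT eligible to participate in Part C if they meet ANY of the exclusion criteria described in Section 4.2 B".

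On timing, Section 6.1 C says that subjects coming from Part B "may consent to the Part C Patient-Led Under Medical Supervision Cardioversion Study prior to or after discharge". Section 6.2 C tells certified subjects that "they must return to the clinic for refresher training at least every 3 months". Section 6.3 C has them return for dosing "for a single recurrent episode(s) of paroxysmal AF within 8 months of signing consent". Sections 6.3 C and 6.4 C end participation at Day 5 after treatment or at 8 months after consent, whichever is earlier.

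**The concern.** The restriction is anchored to two events, consent and the start of inhalation. In Part B these fall in the same visit. In the patient-led study they are separated by training, discharge home and a wait for a recurrence that may never be treated. Taken over unchanged, a short hold before dosing becomes a ban lasting months.

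That collides with criterion 17. A subject may be eligible because as-needed bronchodilator use keeps the asthma controlled, yet may not use it from the day of consent. A site that follows the text withholds routine asthma medication. A site that does not follow it has departed from a stated restriction, and Section 14.1 requires strict adherence and asks for deviations to be explained and documented.

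Two lesser points come from the same cross-reference, through Section 5.4.3 B. Fasting is set to begin once consent is given. The limits on exercise, caffeine and alcohol run to end of study, which for an untreated patient-led subject is 8 months after consent.

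**Working it through.** The plan states no figure to reproduce. The check compares the consent-to-inhalation interval in each setting and asks whether any Part C text narrows it.

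| | Part B and Part C medically-led | Part C patient-led |
|---|---|---|
| When consent is signed | Only after presentation with symptomatic AF (6.1.2.2 B) | Around or after the earlier treatment, before any recurrence (6.1 C) |
| Consent at the treatment visit | Yes, same visit | None; Table 5 marks consent once, ahead of training |
| Minimum time to dosing | 45 minutes of monitoring after consent (7.1 B) | Not stated from consent |
| Maximum time to dosing | Not stated; same-day screening and dosing | 8 months from consent (6.3 C) |
| If not dosed | Early termination (5.5 B) | End of study at 8 months (6.3 C, 6.4 C) |

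1. **Length of the ban.** 8 months × 365.25/12 days per month = 243.5 days, about 243 days, against a same-day hold of at least 45 minutes in Part B.

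2. **Is a long wait intended?** Yes. Section 6.2 C requires refresher training at least every 3 months, with contact about monthly.

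3. **Can dosing fail to occur?** Yes. SAP Section 9.2.5.2 has an end-of-study category for subjects who complete 8 months without treatment. SAP Section 1.1.2 reports 18 subjects enrolled and 3 treated, so 18 − 3 = 15 were not dosed (15/18 = 83%). For them the ban's own end point never arrives, and it lapses only when participation ends.

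4. **Does Part C narrow the window?** No. Section 5.4 C contains only the cross-reference. Part C uses consent to mean the patient-led consent: the 8-month clock in 6.3 C and adverse event capture in 9.1 C both run from it.

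5. **Which subjects are caught?** Those with asthma who use an as-needed bronchodilator. Steroid control under criterion 17 is not barred.

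6. **Would a visit-based hold match Part B?** Closely. Before patient-led dosing the subject's rhythm must be confirmed as one that "remains in AF for at least 30 minutes prior to dosing". A hold starting at arrival would therefore last at least about 30 minutes, against at least 45 minutes in Part B.

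**The case against.** The strongest reply is that the restriction should be read by its purpose. Part B also has an early consent: under Section 6.1.2.1 B, subjects not in AF may sign a pre-study screening consent and wait for an episode. Nobody would take the ban to cover that wait, so consent must mean the one close to dosing, and the same reading makes the patient-led ban a treatment-visit hold. Eligibility is also rechecked before patient-led dosing (Section 4 C), and criterion 17 still admits as-needed users at that point, which suggests that use during the wait was expected. The training procedure and patient instructions, which are not among the documents, may deal with the matter.

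This probably describes the intent, but it does not repair the text. Part B separates the two consents explicitly and places subjects who are waiting under institutional standard of care. Part C has one patient-led consent, none at the treatment visit, and no equivalent sentence on the wait. The recheck under criterion 17 sharpens the conflict, because it shows that the protocol accepts a use that another section prohibits. The duty to treat adverse events (Section 9.1.1 B) and the immediate-hazard provision (Section 14.1) limit harm in an acute episode but do not cover routine as-needed use.

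Some of the reply stands. The purpose given for fasting, to facilitate anesthesia if needed, confines it in practice to the treatment visit. The exercise, caffeine and alcohol items appear under recommendations and tie their end to the Day 5 assessments, which points to the treatment episode. Both are secondary. The practical harm is unknown.

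**Conclusion.** The concern holds. Read literally, the protocol admits subjects whose asthma is controlled with an as-needed bronchodilator and then bars that medication for up to 8 months in the patient-led study. This rests on two readings: that consent in Part C means the patient-led consent, and that the medically-led dose does not count as the inhalation that ends the ban. Both follow from the protocol treating the patient-led study as a distinct study with its own consent and dosing.

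The severity is minor. Part C is exploratory, and no endpoint, population or primary analysis is affected. The documents do not give the number of patient-led subjects with asthma or bronchodilator use; with 18 enrolled it lies between 0 and 18. Confidence in the wording fault is high. Whether anyone was affected cannot be judged from the documents.

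**What to change.** Leave Section 5.4 B unchanged and keep the cross-reference in 5.4 C for the medically-led study. Add for the patient-led study:

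> The bronchodilator restriction in 5.4.1 B starts when the subject arrives at the clinic for the recurrent episode and ends at the start of inhalation; as-needed use while waiting for a recurrence is allowed. The fasting recommendation also starts on arrival. The exercise, caffeine and alcohol rules in 5.4.3 B apply from Day 1 through Day 5 of the patient-led treatment.

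This keeps a hold before dosing close to that in Part B and removes the conflict with criterion 17. The cost is three sentences. No patients, procedures or data are added, since Section 6.2 C already has staff check concomitant medications about monthly during the wait.
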